#### 11.3.1.2 Time to UC worsening

Worsening of the UC is defined as a 2-point increase from the screening TMS with 3 days of continuous rectal bleeding confirmed by flexible sigmoidoscopy with an endoscopy sub-score of 2 points or higher.

Descriptive statistics will be presented for the time to UC worsening (*Table 14.2.2.1 and 14.2.2.2*). Time will be calculated in two different ways: from BIS and from BOLS.

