1.3. Rationale for the clinical study and study design

Phase IIb study (ABX464-101) aimed at evaluating the efficacy and safety of ABX464 given at a fixed dose of 50mg once daily versus placebo in patients with moderate to severe active UC who have failed or are intolerant to immunomodulators, anti-TNF α or corticosteroids was conducted in Belgium, France, Germany, Austria, Poland, Hungary.

32 patients were randomized (23 ABX464 patients/9 placebo). The principal study results are presented below.

A strong efficacy signal was observed with ABX464 50 mg:

- Clinical Remission rate of 35.0 % of ABX464 patients (Placebo = 11.1%)
- Mucosal Healing rate of 50.0 % (p=0.03) of ABX464 patients (Placebo = 11.1%)
- Clinical Response rate of 70.0 % of ABX464 patients (Placebo = 33.0%)

Same results were also observed in Total and Partial Mayo Score, as depicted in the following graphs

[figure not shown]

Figure 3: Mean change in Total and Partial Mayo Score in ABX464-101 study

At the end of the completed 2 months induction treatment study, 22 Patients (15 previously treated with ABX464 and 7 on placebo) were enrolled into the open-label maintenance study with ABX464 50mg daily (ABX464-102) regardless of what treatment they had previously received. An interim analysis of this maintenance study was performed after all patients had completed at least 12 months dosing in the maintenance study, with a mean ABX464 treatment duration in the maintenance study of 422 days.

The interim analysis used the Month 12 Per Protocol (M12 PP) dataset which included all subjects that had a Month 12 visit. Of the 22 subjects, 3 subjects were excluded from the M12 PP Set: 2 subjects from the ABX464 induction group (one who withdrew due to lack of efficacy at M1 of the maintenance study and one who was lost to follow-up) and 1 subject from the placebo induction group (grade 2 headache at month 4), resulting in 19 subjects analyzed in the efficacy M12 PP set at baseline. Of the nineteen subjects in the set, sixteen had had a Month 12 endoscopy performed which forms part of the Total Mayo score (TMS).

Clinical remissions obtained at the end of the induction study were durable and the rates further improved during the maintenance phase, as additional subjects achieved clinical remission for 12 months treatment.

All patients who had an endoscopy performed, had an endoscopic sub-score of 0 or 1. 12/16 patients were in clinical remission at month 12.

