2.4. Secondary Endpoints

The secondary endpoints of this study are:

- The change from Day 0 in Total Mayo Score.
- The change from Day 0 in Partial Mayo Score.
- The time to UC worsening.
- The change from Day 0 in fecal calprotectin, CRP levels and ESR.
- The scores and changes from Day 0 in SF-36 Questionnaire scores.
- The miR-124 expression at month 12, month 36 and month 48.
- The number of incidences of treatment-emergent serious adverse events.
- The number of incidences of treatment-emergent adverse events of special interest.
- The number of incidences of adverse events leading to investigational product discontinuation.
- The number of incidences of specific laboratory abnormalities.
- Percentage of subjects reaching clinical remission at M12, M36, and M48.
- Percentage of subjects reaching clinical response at M12, M36, and M48.
- Percentage of subjects reaching endoscopic improvement at M12, M36, and M48.
- Percentage of subjects reaching endoscopic remission at M12, M36, and M48.
- Percentage of subjects reaching corticosteroid-free clinical remission at M12, M36, and M48.

The echocardiography secondary endpoints^[9] are:

- Absolute (%) change-from-previous echocardiogram of Left ventricle Ejection Fraction (LVEF) as measured by 2-dimensional echocardiography
- Number of subjects with a clinically relevant reduction (change-from-previous echocardiogram) of LVEF, defined as by > 10% reduction (absolute percentage points) to a value < 50%

- Absolute (%) change in Global Longitudinal Strain (GLS) from-previous echocardiogram
- Number of subjects with a relative percentage reduction in GLS by > 15% from the previous value
- Number of subjects with a reduction of LVEF > 10% (absolute percentage points) to a value $\geq 50\%$ with an accompanying fall in GLS > 15%
- Number of subjects with reduction in LVEF by > 10% (absolute percentage points) to a value $\geq 50\%$
- Changes from previous echocardiography of other echocardiographic parameters as described in a standard protocol, including 2-dimensional volumes, RV size and systolic function and valve function.

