5.3.8. Partial/Total Mayo Score

The Total Mayo score is the most commonly used index in clinical trials and consists of 4 items: stool frequency, rectal bleeding, flexible sigmoidoscopic examination, and a physician global assessment of disease activity (Appendix#3).

A non-invasive 9-point Mayo or partial Mayo Score (pMS) incorporates stool frequency, rectal bleeding, and the physician's global assessment of disease activity. The partial Mayo Score has been found to correlate closely with the full Mayo score and to independently have strong discriminative and construct validity and responsiveness to change in disease activity.

Modified Mayo Score (MMS) consists of 3 items: stool frequency, rectal bleeding, flexible sigmoidoscopic examination) and partial Modified Mayo Score (pMMS) consists of only 2 items: stool frequency and rectal bleeding. Either the Partial or the Total Mayo score will be completed at each subject visit by the Investigator.

Partial modified or modified Mayo score will also be used in descriptive analysis and for efficacy evaluation.

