6.3. Administration and Dosing

6.3.1. Administration of the investigational product

Subjects will be dosed with a daily dose of 50 mg that is 1 capsule every day.

Subjects will be orally dosed in fed condition (regular breakfast) with a cup of water.

A subject diary, in which the subject should report the number of capsules taken and the intake time, will be given to the subject at baseline. Moreover, this diary will enable the subject to report also potential discomfort or side effects s/he could experience.

The last study treatment intake should be the day before M48 visit.

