 - Worsening of the UC defined as a 2-point increase in the pMMS, with pMMS ≥ 4 on 2 separate occasions 7 day-apart and confirmed by an endoscopy sub score of 2 points or higher; subject who would experience a treatment failure during the study may be withdrawn at any time. S/he will have to be treated according to standard of care as soon as s/he is discontinued from study treatment because of study withdrawal;
 - Withdrawal of consent;
 - Pregnancy;
 - Patients included with a history of cardiac ischemic disease and/or congestive heart failure will be discontinued from the study, will perform the End of Study Visit 4 weeks after last study drug administration and will then be treated according to the standard of care upon study treatment interruption.
 - Administrative reasons from Sponsor.

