Appendix 3: Mayo Score (Ulcerative Colitis)

Components of the Mayo Score	
Stool frequency	
0	Normal
1	1–2 stools/day more than normal
2	3–4 stools/day more than normal
3	5 or more stools/day more than normal
Rectal bleeding	
0	None
1	Visible blood with stool less than half the time
2	Visible blood with stool half of the time or more
3	Passing blood alone
Mucosal appearance at endoscopy	
0	Normal or inactive disease
1	Mild disease (erythema, decreased vascular pattern, mild friability)
2	Moderate disease (marked erythema, absent vascular pattern, friability, erosions)
3	Severe disease (spontaneous bleeding, ulceration)
Physician rating of disease activity	
0	Normal
1	Mild
2	Moderate
3	Severe

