| Worsening of UC                  | xx (xx.x%)   | xx (xx.x%)                                     | xx (xx.x%)      |
| Major protocol violation         | xx (xx.x%)   | xx (xx.x%)                                     | xx (xx.x%)      |
| Patient's decision               | xx (xx.x%)   | xx (xx.x%)                                     | xx (xx.x%)      |
| Withdrawal of consent            | xx (xx.x%)   | xx (xx.x%)                                     | xx (xx.x%)      |
| Etc                              |  |  |                 |

The denominator for each percentage is the number of patients in the column. Completed defined as performed follow-up visit.

Source: Listing 16.2.2

Path\Filename

Page x/y

ABX464-102

ddMMMyyyy HH:MM

Table 14.1.3 Demographic, Baseline and Disease Characteristics (OC Set)

|                                  |                    | 50mg ABX464 (101) +
50mg ABX464 (102)
(N=xx) | Placebo (101) +
50mg ABX464 (102)
(N=xx) | Total
(N=xx) |
|----------------------------------|--------------------|--|--|-----------------|
| Age (years)                      | n                  | xx   | xx   | xx              |
|                                  | Mean               | xx.xx  | xx.xx  | xx.xx           |
|                                  | SD                 | xx.xx  | xx.xx  | xx.xx           |
|                                  | Median             | xx.xx  | xx.xx  | xx.xx           |
|                                  | Minimum            | xx.x   | xx.x   | xx.x            |
|                                  | Maximum            | xx.x   | xx.x   | xx.x            |
| Gender                           | n                  | xx   | xx   | xx              |
|                                  | Male               | xx (xx.x%)   | xx (xx.x%)                                     | xx (xx.x%)      |
|                                  | Female             | xx (xx.x%)   | xx (xx.x%)                                     | xx (xx.x%)      |
| Childbearing*                    | Yes                | xx (xx.x%)   | xx (xx.x%)                                     | xx (xx.x%)      |
|                                  | No                 | xx (xx.x%)   | xx (xx.x%)                                     | xx (xx.x%)      |
| Reason for non-
Childbearing* | Post-menopausal    | xx (xx.x%)   | xx (xx.x%)                                     | xx (xx.x%)      |

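### The SAP's definition of UC worsening needs a bleeding duration that no described assessment records, and it departs from the protocol's definition without saying so

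*SAP*

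**What the plan says.** Protocol 2.4 lists "The time to UC worsening" among the secondary endpoints. SAP 11.3.1.2 defines the event as a "2-point increase from the screening TMS with 3 days of continuous rectal bleeding confirmed by flexible sigmoidoscopy", with an endoscopy sub-score of at least 2. Time is counted from two origins: the start of the induction study (BIS) and the start of this study (BOLS).

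The protocol has its own definition, used as a discontinuation criterion in section 7.2 and in the synopsis. It begins "Worsening of the UC defined as a 2-point increase in the pMMS". It then requires a pMMS of at least 4 on two occasions a week apart, and the same endoscopic confirmation. It sets no condition on how long bleeding lasts.

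SAP 1.2 lists the changes from the protocol, including those to clinical response and corticosteroid-free remission. The change to UC worsening is not among them.

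**The concern.** An event can be derived only if each of its parts is recorded. The SAP joins three conditions, and the middle one concerns consecutive days. If no source holds that information, the person programming the endpoint must either treat the condition as unmet or substitute something the SAP does not state. The first loses events. The second means that the endpoint was not fixed in advance.

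The undeclared departure from the protocol adds a second problem. The shell for Table 14.1.2 has "Worsening of UC" as a reason for withdrawal, and such withdrawals follow the protocol's criterion. Table 14.2.2.1 follows the SAP's. The two tables may then disagree about the same patient, with nothing in the SAP to explain why.

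**Working it through.** The plan states no event count, rate or power for this endpoint, so there is no figure to reproduce. The check traces each condition to a data source and then compares the two definitions.

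**1. Is there a source for consecutive days of bleeding?**

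| Possible source | What it holds |
|---|---|
| Mayo bleeding item (protocol Appendix 3) | A 0–3 grade; grade 1 is "Visible blood with stool less than half the time". No day count, no continuity |
| When it is scored (protocol 5.3.8) | "Either the Partial or the Total Mayo score will be completed at each subject visit by the Investigator" |
| Visit schedule (protocol 3.1.1, 5.1) | Weekly, then two-weekly, monthly and quarterly; never daily |
| Patient diary (protocol 6.3.1) | "the subject should report the number of capsules taken and the intake time", plus open-ended discomfort or side effects |
| Adverse-event records (protocol 8) | Disease progression is kept out of adverse-event reporting and goes to the efficacy part of the eCRF, whose content is not described |
| Symptom e-diary (protocol 1.2.5) | Described for study ABX464-103 only |
| Listing 16.2.6.1 | Sub-scores by visit |
| Listing 16.2.6.2 | The resulting times only |

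None of these records bleeding duration. SAP 10.4 allows last-observation-carried-forward for continuous values and non-responder imputation for dichotomous values in the NRI Set, and rules out any other imputation. It does not say how either would apply to a missing part of an event.

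**2. How do the two definitions compare?**

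| Part | Protocol 7.2 | SAP 11.3.1.2 |
|---|---|---|
| Score | pMMS: stool frequency + bleeding | Total Mayo Score (TMS): those two + physician rating + endoscopy |
| Rise | 2 points, reference visit not named | 2 points from screening |
| Level | pMMS ≥ 4, twice, 7 days apart | None |
| Bleeding duration | None | 3 days |
| Endoscopy | Sub-score ≥ 2 | Sub-score ≥ 2 |

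Screening is not tied to BIS or BOLS in SAP 5.1, although SAP 3.4 labels Visit 1 as both screening and Day 0.

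**3. Can a patient meet the protocol rule and miss the SAP event?** Yes, in two ways. Read each rise as at least 2 points, and write the sub-scores in the order stool, bleeding, physician, endoscopy.

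- *Bleeding.* From (1, 0, 1, 1) to (3, 1, 2, 2): pMMS goes from 1 to 4 and TMS from 3 to 8. With a second reading a week later, the protocol rule is met. The SAP's TMS and endoscopy conditions are met too, but a bleeding grade of 1 does not show three continuous days.
- *Score.* From (1, 1, 3, 3) to (3, 1, 3, 2): pMMS goes from 2 to 4, but TMS goes only from 8 to 9. The SAP event fails on TMS alone, whatever the bleeding.

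The number of score combinations that meet the protocol's thresholds can be counted. Six (stool, bleeding) pairs reach pMMS ≥ 4: (1,3), (2,2), (3,1) at 4; (2,3), (3,2) at 5; (3,3) at 6. The baseline pairs at least 2 points lower number 6, 10 and 13 respectively.

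- Stool–bleeding transitions: 3×6 + 2×10 + 1×13 = 51.
- The other items contribute 4 (later physician rating) × 2 (later endoscopy 2 or 3) × 16 (baseline physician and endoscopy) = 128.
- Total: 51 × 128 = 6,528.
- With a later bleeding grade of 1, from the pair (3,1) only: 6 × 128 = 768, or 768/6,528 = 11.8%.
- With a TMS rise below 2, by full enumeration: 878, or 878/6,528 = 13.4%.

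These are shares of possible score combinations, not patient probabilities. They show that the gap is possible and do not estimate how often it occurs.

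**4. How often is TMS available?** Scheduled visits after Day 0 number 6 (D7 to D56) + 22 (M3 to M24) + 8 (M27 to M48) = 36. Sigmoidoscopy is mandatory at four (M2, M24, M36, M48), so 32 need not yield a TMS. Both definitions need endoscopic confirmation, so this alone does not separate them.

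**The case against.** The strongest reply is that the CRF specifications, dated in SAP 1.1, are not available here, and protocol section 8 says that disease progression is documented in an efficacy section of the eCRF. A field for bleeding duration could exist there. Listing shells are weak evidence that it does not: SAP 15 allows layouts to change, and SAP 11.3 promises listings that show how time to UC worsening was derived. This stands. It limits the claim to what the documents describe, and it rules out the inference that the endpoint cannot be derived or must yield zero events.

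A reader might also infer that the clause makes durability look better. The documents support that only for the event count, and only if unrecorded duration is treated as not met. Under a proxy the direction is unknown. Table 14.2.2.1 reports means and quartiles with no censoring rule, so with no qualifying events it would show no time estimate at all.

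A reader might point to the patient "one who withdrew due to lack of efficacy at M1 of the maintenance study" as a lost event. The documents do not say that this patient worsened. Lack of efficacy need not mean a 2-point rise, and the protocol's rule would not necessarily count it either. One patient in 22 is 1/22 = 4.5 percentage points, but no particular patient is shown to be affected.

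Finally, the analysis is descriptive, the primary safety endpoint is untouched, and deterioration remains visible in the Mayo scores, the remission rates and the withdrawal reasons. This limits the importance of the point but leaves the undeclared difference between the two definitions in place.

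**Conclusion.** The point holds in this form: SAP 11.3.1.2 relies on a bleeding duration with no described data source, and it replaces the protocol's definition of UC worsening without declaring the change. A patient withdrawn for worsening as the protocol defines it can be absent from the SAP's worsening events. If missing duration counts as not met, events are under-counted; if a proxy is used, the endpoint is not pre-specified.

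The size in patients cannot be given, because no event data or CRF content are available. The conclusion assumes that the protocol and SAP describe all the planned bleeding assessments; a CRF field for duration would remove the data-source part but not the undeclared difference. It should be settled before database lock, as an issue limited to one descriptive secondary endpoint.

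**What to change.** Before database lock, choose one of two routes. Which clinical definition applies is the sponsor's decision.

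- *Reconcile.* Bring SAP 11.3.1.2 and the protocol's definition (section 7.2 and synopsis) into agreement, so that the time-to-worsening event rests on components that are recorded. Name the reference visit for the rise. If two readings a week apart remain part of the rule, say how unscheduled visits supply the second, since scheduled visits are further apart than that after the first month.
- *Keep the SAP rule.* Name the data source for bleeding duration, state what happens when it is missing, say which visit screening means, and declare the change in SAP 1.2.

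On either route, state how withdrawals recorded as "Worsening of UC" enter the endpoint, and show the event components by patient in Listing 16.2.6.2, so that Tables 14.1.2 and 14.2.2.1 can be checked against each other.

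The cost is SAP wording and a small derivation change on data already collected, unless the sponsor keeps a component that turns out not to have been recorded. The downside is that the event count may change.

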### 1.2 CHANGES FROM PROTOCOL

- The echocardiography secondary endpoints will be included in a separate report.
- Sustained clinical remission and sustained endoscopic remission/improvement will be summarized as part of the secondary endpoints.
- Observed Cases (OC) Set and Non-responder Imputation (NRI) Set are defined for populations instead of the populations defined in the protocol.
- In the definition of corticosteroid-free clinical remission (Section 11.3.1.6), time interval is changed from 12 weeks to 90 days for consistency with other Abivax studies.
- In the definition of clinical response (Section 11.3.1.6), Modified Mayo Score is used instead of Total Mayo Score for consistency with other Abivax studies.
- All efficacy variables will be summarized based on the following subgroups:
  - Patients being in clinical response at BOLS and not being in clinical response at BOLS
  - Patients previously treated with biological drugs and naive from biological drugs.
- In the Synopsis and Section 2.4 of the protocol, M24 is missing from the list of timepoints for clinical remission, clinical response, endoscopic improvement, endoscopic remission and corticosteroid-free clinical remission inconsistently with further sections. This timepoint is included in the current SAP to ensure that these secondary endpoints are analysed for all required timepoints.

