## 14.2 LIST OF FIGURES

Not applicable.

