
BOLS: Day 56 of ABX464-101 study

---

Source: Listing 16.2.6.1

Path\Filename

Page x/y

*Programming Note: Include Total Mayo Scores and Partial Mayo Scores.*

*Please present subgroups in the following order:*

- All patients
- Patients being in clinical response at Baseline Open-Label Study (BOLS)
- Patients not being in clinical response at Baseline Open-Label Study (BOLS)

---

Version Date 20 MAY 2021

Template STATt004

Page 39 of 97

- *Patients previously treated with biological drugs*
- *Patients naive from biological drugs*

This layout also applies to:

*Table 14.2.1.2 Change from Baseline: Mayo Score (MS, pMS, MMS and pMMS) (NRI Set)*

*Table 14.2.1.3 Change from Baseline: Components of the Total Mayo Score (OC Set)*

*Table 14.2.1.4 Change from Baseline: Components of the Total Mayo Score (NRI Set)*

*Programming Note for Table 14.2.1.3 and 1.4: Components: Stool frequency, Rectal bleeding, Physician rating of disease activity and Mucosal appearance at endoscopy – central reading*

ABX464-102

ddMMMyyyy HH:MM

Table 14.2.2.1 Time to UC Worsening (OC Set)

<Subgroup>

|                                       |           | 50mg ABX464 (101) +
50mg ABX464 (102)
(N=xx) | Placebo (101) +
50mg ABX464 (102)
(N=xx) | Total
(N=xx) |
|---------------------------------------|-----------|--|--|-----------------|
| Time to UC worsening from BIS (Unit)  | n         | xx (xx.x %)  | xx (xx.x %)                                    | xx (xx.x %)     |
|                                       | Mean      | xx.xx  | xx.xx  | xx.xx           |
|                                       | 95% CI    | xx.xx – xx.xx                                      | xx.xx – xx.xx                                  | xx.xx – xx.xx   |
|                                       | SD        | xx.xx  | xx.xx  | xx.xx           |
|                                       | Minimum   | xx.x   | xx.x   | xx.x            |
|                                       | Maximum   | xx.x   | xx.x   | xx.x            |
|                                       | Median    | xx.xx  | xx.xx  | xx.xx           |
|                                       | Quartiles | xx.xx – xx.xx                                      | xx.xx – xx.xx                                  | xx.xx – xx.xx   |
| Time to UC worsening from BOLS (Unit) | n         | xx (xx.x %)  | xx (xx.x %)                                    | xx (xx.x %)     |

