## Listing 16.2.6.2 Efficacy Data: Time to UC Worsening

| Treatment  | Centre/ Patient number | Time to UC worsening
(unit) |              |
|--|------------------------|--------------------------------|--------------|
|  |                        | from
BIS                    | from
BOLS |
| xxxxxx   | xxxx-xxx               | xx                             | xx           |
| Etc  |                        |                                |              |
| <hr/> BIS: Day 0 of ABX464-101 study
BOLS: Day 56 of ABX464-101 study <hr/> |                        |                                |              |

Path\Filename

Page x/y

*Programming Note: For the Treatment column, please present treatment for ABX101 + ABX102 study consistently to the table headers.*

ABX464-102

ddMMMyyyy HH:MM

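### Time to UC worsening is planned as a mean with SD and CI and no rule for patients who never worsen or leave early; a Kaplan-Meier summary would suit the unequal follow-up

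*SAP*

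**What the plan says.** Protocol 2.4 lists time to UC worsening as a secondary endpoint and does not define it there.

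SAP 11.3.1.2 defines worsening as "defined as a 2-point increase from the screening TMS with 3 days of continuous rectal bleeding confirmed by flexible sigmoidoscopy", with an endoscopy sub-score of at least 2. On analysis it says "Descriptive statistics will be presented for the time to UC worsening", with time counted both from the induction baseline (BIS) and from BOLS. The shell for Table 14.2.2.1, reused for the NRI Set in Table 14.2.2.2, has rows for n (%), mean, 95% CI, SD, minimum, maximum, median and quartiles. It has no row for event-free patients or for numbers at risk. Listing 16.2.6.2 prints one time per origin for each patient, with no event or censoring flag. SAP 14.2 plans no figures.

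SAP 10.4 carries the last observation forward for missing continuous values in both sets, counts missing dichotomous values as non-response in the NRI Set, and allows no other imputation.

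The protocol's only description of worsening is among the discontinuation criteria in 7.2 (and the synopsis): "Worsening of the UC defined as a 2-point increase in the pMMS", with further conditions. The same item adds "subject who would experience a treatment failure during the study may be withdrawn at any time", so withdrawal after failure is optional. SAP 1.2 declares other definition changes, for example "In the definition of clinical response (Section 11.3.1.6), Modified Mayo Score is used instead of Total Mayo Score", and does not mention worsening.

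**The concern.** A time-to-event endpoint with incomplete follow-up needs a stated treatment of patients without an event. The planned statistics can be computed in two ways. One summarises only the patients who worsened. The other gives event-free patients their follow-up time. The SAP text allows both, and on neither do the mean and its CI estimate time free of worsening.

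This is the plan's time-to-event measure of durability over 48 months. An events-only mean could look much the same whether worsening was rare or common. A follow-up-time mean would move with dropout.

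Separately, because the two documents describe worsening differently, a patient counted under worsening of UC in the withdrawal table (Table 14.1.2) may have no event in Table 14.2.2.1, and the reader would find no explanation.

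**Working it through.** The documents give no event count, risk or median for this endpoint, so there is no planned figure to reproduce. All risks and dropout rates below are assumed, with constant hazards and a 48-month horizon.

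**Inputs from the documents**
- 22 enrolled, and 3 excluded from the month 12 per-protocol set, leaving 19 (protocol 1.3). One of the 3 withdrew for lack of efficacy at month 1.
- 14 treated for more than 3 years, in a paragraph dated 30 November 2021 (protocol 1.2.5). 14/22 = 63.6%, so up to 36.4% were not documented beyond 3 years.
- Planned treatment of 48 months (protocol 3.1.1).

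**Step 1. Do the general rules fill the gap?** Last observation carried forward needs an earlier value, and a single event time per patient has none. The non-responder rule applies to dichotomous values only. Neither assigns a time to an event-free patient.

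**Step 2. Events-only reading, full follow-up.** With 48-month risk p, λ = −ln(1−p)/48. The mean among patients with an event is 1/λ − 48(1−p)/p. The mean time free of worsening up to 48 months is p/λ.

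| Assumed p | λ per month | Events-only mean (months) | Mean event-free time to M48 (months) |
|---|---|---|---|
| 10% | 0.002195 | 455.6 − 432.0 = 23.6 | 45.6 |
| 50% | 0.014441 | 69.2 − 48.0 = 21.2 | 34.6 |

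A fivefold change in risk moves the events-only mean by 2.4 months and the event-free time by 11.0. At p = 10% the chance of at most one event among 22 is 0.9^22 + 22 × 0.1 × 0.9^21 = 0.34. With one event or none, no SD or CI could be computed.

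**Step 3. Follow-up-time reading.** Take p = 20% (λ = 0.004649) and let other exits have hazard c = −ln(1−q)/36, where q is the assumed dropout by month 36. With H = λ + c, the mean is (1 − exp(−48H))/H.

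| Assumed q | H | Mean (months) |
|---|---|---|
| 0% | 0.004649 | 43.0 |
| 20% | 0.010847 | 37.4 |
| 36% | 0.017046 | 32.8 |

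The worsening risk is the same in all three rows. The converse also holds, because only the sum H matters. A worsening risk of 10% by month 48 with other exits at 0.01256 per month (45.3% by month 48) gives H = 0.01475 and a mean of 34.4 months. Swapping the two hazards, so that 45.3% worsen and 10% leave for other reasons, gives the same 34.4.

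**Step 4. The n (%) row.** If n counts events, the row shows (λ/H)(1 − exp(−48H)). At p = 20% this is 20% with no dropout and 0.2727 × 0.5588, about 15%, at q = 36%. It carries information on frequency, but as a crude proportion that ignores unequal follow-up.

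**Step 5. The two descriptions of worsening**

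| | SAP 11.3.1.2 | Protocol 7.2 |
|---|---|---|
| Purpose | Endpoint | Discontinuation criterion |
| Score | Total Mayo Score, up 2 points | pMMS, up 2 points |
| Reference value | 'Screening' | Not stated |
| Further condition | 3 days of continuous rectal bleeding | pMMS at least 4, twice, a week apart |
| Endoscopy sub-score | At least 2 | At least 2 |

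SAP 5.1 names only BIS and BOLS as baselines. The SAP 3.4 visit table labels the first visit as screening and day 0 together, and SAP 5.1 makes BOLS the default, so BOLS looks intended but is not stated.

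**The case against.** **A reader could identify the method used.** This largely stands. The n (%) row set against the column N, together with the times in Listing 16.2.6.2 and the dose and withdrawal dates in Listing 16.2.2, would mostly show which reading was applied among 22 patients. It is tempting to say that the result would be opaque. The documents do not support that: the fault is a missing pre-specification and an unsuitable summary.

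**An events-only mean has a meaning.** It describes when worsening occurred among those who worsened, and n (%) describes how often. That is fair if labelled, but the two rows together still give no event-free percentage that allows for unequal follow-up.

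**The illustrations depend on their set-up.** If the total exit hazard is held fixed, a mean that depends only on that total cannot change with the share due to worsening. It would be wrong to infer that the follow-up-time mean never responds to worsening. If worsened patients stay in the study, as protocol 7.2 permits, and other exits have hazard 0.01256, it falls from 34.4 to 26.9 months as assumed risk rises from 10% to 50%. What stands is that the mean cannot separate worsening from dropout. Also, 14 of 22 is a lower bound on those passing 3 years, because it is a count at a data cut-off.

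**The definition in 7.2 is not the endpoint definition.** This stands. It is a discontinuation rule not tied to the endpoint, and protocol section 9 leaves technical elaboration to the SAP. The declared change to clinical response alters an explicit protocol definition, so it is not a like-for-like precedent. A reader might infer that the SAP changed the protocol's endpoint without declaring it; the documents do not establish that.

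**Conclusion.** The concern holds for the method. SAP 11.3.1.2 and its two shells apply complete-data statistics to an endpoint with unequal follow-up and give no rule for patients without an event. Under constant hazards, the events-only mean stays between 21.2 and 23.6 months for assumed risks of 10% to 50% with full follow-up. The follow-up-time mean moves by about 10 months (43.0 to 32.8) on dropout alone at an assumed 20% risk. These figures show the mechanism and do not forecast the trial's results, because no worsening rate is documented.

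The definition point is secondary. The two descriptions differ in score, reference value and confirming condition, and this needs reconciliation or one explanatory sentence. No view is taken on which clinical rule is right.

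The stakes are modest: one descriptive secondary endpoint in an uncontrolled study whose primary objective is safety.

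**What to change.** - **SAP 11.3.1.2 and Tables 14.2.2.1/14.2.2.2:** replace the mean, SD and CI of the mean with a Kaplan-Meier summary from BOLS. Show the number of events, numbers at risk, event-free percentage with 95% CI at M12, M24, M36 and M48, and the median if reached.
- **Event and censoring dates:** pre-specify both. Event-free patients could be censored at the last visit or at the last endoscopy-based assessment. The choice is debatable. The Total Mayo Score exists only where an endoscopy was done, yet endoscopy is mandatory only at M2, M24, M36 and M48, so the endoscopy rule discards observed follow-up. Choose one and use the other as a sensitivity analysis if wanted.
- **Listing 16.2.6.2:** add an event/censor flag.
- **Definition:** reconcile SAP 11.3.1.2 with protocol 7.2 or state why they differ, and replace 'screening' with the named baseline.

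The cost is a short SAP amendment, revised shells and one listing column, using data already collected. Protocol section 9 allows documented SAP amendments before final database lock. The downside is imprecision, which the report should state. In simulations with 22 patients, constant hazards, exits calibrated to 14 of 22 passing 36 months, and log-log intervals, the median width of the 95% CI for the event-free percentage at M48 was about 37 to 41 points. Those simulations are not described as using endoscopy-based censoring, so the width under that rule may differ.
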